6.0 STRATIFICATION FACTORS

Patients will be stratified according to disease status defined as follows:

- (1) Patients with MDS transformed to AML
- (2) Refractory or relapsed patients with previous remission < 6 months.

7.0 TREATMENT PLAN

For treatment or dose modification questions, please contact [name] at [name], or if [name] is not available, [name] at [name]. For dosing principles or questions, please consult the SWOG Policy #38 "Dosing Principles for Patients on Clinical Trials" at <http://swog.org> (then click on "Policies and Manuals" under the "Visitors" menu and choose Policy 38).

7.1 Good Medical Practice

The following pre-study tests should be obtained within 28 days prior to registration (both Induction and Consolidation) in accordance with good medical practice. Results of these tests do not determine eligibility and minor deviations would be acceptable if they do not affect patient safety in the clinical judgment of the treating physician. The Study Chair must be contacted if there are significant deviations in the values of these tests. If an individual test is considered to be unnecessary, the rationale for not conducting the test must be documented in the medical record.

- a. Chest X-ray (posterior-anterior and lateral) and EKG.
- b. PT, PTT

7.2 Pre-Medication

While the following pre-treatment medications are recommended, pre-treatment medication may be given at the discretion of the treating physician.

- a. Granisetron, palonosetron or ondansetron prior to chemotherapy on Days 4-7.
- b. Dexamethasone eye drops 0.1%: 2 drops to each eye every 6 hours on Days 3-8 for Induction therapy and Days 3-6 for Consolidation therapy (to prevent conjunctivitis associated with high dose AraC).

7.3 Induction Therapy

Patients should discontinue all other statin treatments while receiving protocol treatment.

A maximum of 1 cycle of Induction therapy will be allowed.

Agent	Dose	Route	Day
Pravastatin*	1,280 mg/day	PO	1-8
Idarubicin	12 mg/m ² /day	IV over 10-15 minutes	4-6
AraC	1.5 g/m ² /day	continuous IV	4-7

* Pravastatin will be provided in 80 mg tablets. Patients may receive 16 tablets/day of pravastatin over 2 hours to achieve total dose.

For patients with a high WBC count at the time of study enrollment, hydroxyurea can be used concurrently at the investigator's discretion, until Day 10 (with Day 1 being the start of pravastatin).

Pravastatin will be administered once daily in the morning on Days 1-8. Neurotoxicity exams should be performed prior to each dose of AraC. AraC should be held and no further doses administered if any signs of cerebellar neurotoxicity are found, and the Study Chair must be contacted.

7.4 Consolidation Therapy

Patients achieving complete remission (CR) as defined in [Section 10.1](#) will be eligible to receive protocol Consolidation therapy, provided they meet the eligibility criteria outlined in [Section 5.2](#), and are registered for Consolidation therapy before beginning Consolidation therapy.

A maximum of 2 cycles of Consolidation therapy will be allowed.

Consolidation Therapy must be initiated no sooner than 30 days and no later than 60 days after the start of Induction therapy (with Day 1 being the start of induction). The second cycle of Consolidation therapy must be initiated no sooner than 30 days and no later than 60 days after the start of the first cycle of Consolidation. Patients must remain in complete remission with an absolute neutrophil count $\geq 1,000/\text{mcl}$ and platelet count $\geq 100,000/\text{mcl}$ before beginning the second cycle of Consolidation therapy. A bone marrow examination to confirm CR is NOT required prior to initiating the second cycle of Consolidation therapy.

Agent	Dose	Route	Day
Pravastatin*	1,280 mg/day	PO	1-6
Idarubicin	12 mg/m ²	IV over 10-15 mins	4-5
AraC	1.5 g/m ² /day	Continuous IV	4-5

* Pravastatin will be provided in 80 mg tablets. Patients may receive 16 tablets/day of pravastatin over 2 hours to achieve total dose.

Pravastatin will be administered once daily in the morning on Days 1-6. Neurotoxicity exams should be performed prior to each dose of AraC. AraC should be held and no further doses administered if any signs of cerebellar neurotoxicity are found. AraC should be held, no further doses administered, and the Study Chair must be contacted.

ECHO or MUGA (whichever was performed at baseline) should be performed prior to each cycle of Consolidation therapy.

7.5 Follow-up

Patients will be followed for date of relapse and date of death. Follow-up will include complete physical examination and CBC with differential and platelets monthly for the first year, every three months for the second and third years, and every 6 months for the fourth and fifth years. Other tests will be performed at the discretion of the treating physician.

7.6 Growth Factors

G-CSF or GM-CSF therapy may be used at the discretion of the treating physician in patients who develop infections while neutropenic, but is discouraged for the sole purpose of accelerating count recovery. (Growth factors should be used in accordance with ASCO guidelines).

7.7 Assessment of Response

A bone marrow aspirate and biopsy will be obtained after completion of Induction therapy at the time of blood count recovery ($ANC \geq 1,000/mcl$, platelets $\geq 100,000/mcl$) or by Day 45, whichever comes first. This aspirate/biopsy, or an additional aspirate/biopsy showing a CR, must be obtained prior to the Consolidation registration (see [Section 5.2a](#)).

7.8 Criteria for Removal from Protocol Treatment

- a. Progressive disease (as defined in [Section 10.2](#)).
- b. Failure to achieve CR after one cycle of Induction therapy.
- c. Ejection fraction drop of $\geq 10\%$ from baseline before either cycle of Consolidation therapy.
- d. Unacceptable toxicity.
- e. Completion of all cycles of protocol therapy (one cycle of Induction and two cycles of Consolidation).
- f. The patient may withdraw from the study at any time for any reason.

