- _____ f. Patients must not have symptomatic congestive heart failure, coronary artery disease, cardiomyopathy, or uncontrolled arrhythmias. Either an echocardiogram or MUGA scan with an ejection fraction $\geq 45\%$ must be obtained within 28 days prior to registration, or within 14 days prior to registration if the patient has received anthracycline in the 28 day window. (Either method for measuring cardiac function is acceptable; however, the same scan must be used throughout treatment and follow-up to monitor the patient for cardiac toxicity.) If the patient has symptoms suggestive of ischemia or congestive heart failure after that cardiac evaluation was done, a repeat study must be obtained prior to registration.
- _____ f. Patients must have a serum creatinine < 2.0 mg/dl within 14 days prior to registration.
- _____ g. Patients must have a total bilirubin $\leq 2.0 \times$ Institutional Upper Limit of Normal (IULN) within 14 days prior to registration, unless the elevation is due primarily to elevated unconjugated hyperbilirubinemia secondary to Gilbert's syndrome or hemolysis and not to liver dysfunction.
- _____ h. Patients must have SGOT (AST) $\leq 3.0 \times$ IULN and SGPT (ALT) $\leq 3.0 \times$ IULN within 14 days prior to registration. Treatment may begin with SGOT/SGPT above those limits, if the abnormalities are thought to be due to the patient's leukemia.
- _____ i. Patients must have Zubrod performance status of 0-2 (see [Section 10.7](#)).
- _____ j. Patients must be ≥ 18 years of age.
- _____ k. Patients must not have clinical evidence of leptomeningeal disease (a spinal tap does not need to be performed).
- _____ l. Patients who are known to be HIV+ may be eligible providing they meet all of the following additional criteria within 28 days prior to registration:
 - 1. Patient must have no history of AIDS defining events.
 - 2. CD4 cells $\geq 500/\text{mm}^3$.
 - 3. Viral load of < 50 copies HIV mRNA/ mm^3 if on cART or $< 25,000$ copies HIV mRNA if not on cART.
 - 4. No zidovudine or stavudine as part of cART.

Patients who are HIV+ and do not meet all of these criteria will not be eligible for this study.

SWOG Patient No. _____

Patient's Initials (L, F, M) _____

5.1 Induction Registration (Step 1) (contd.):

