- _____ m. Patients with prior malignancy (other than AML and MDS/CMML) are eligible. However, the patient must be in remission from the prior malignancy and have completed all chemotherapy and radiotherapy at least 6 months prior to registration. Except for AML and MDS treatment, all treatment related toxicities must have been resolved.

NOTE: For patients with prior history of malignancy who have received anthracyclines or mediastinal/pericardial radiation in the past, the risk versus benefit of therapy should be weighed, particularly in the setting of receiving consolidation therapy.

- _____ n. Patients must not have a systemic fungal, bacterial, viral or other infection that is not controlled (defined as exhibiting ongoing signs/symptoms related to the infection and without improvement, despite appropriate antibiotics or other treatment).
- _____ o. Pretreatment cytogenetics must be performed on all patients. Collection of pretreatment specimens must be completed within 28 days prior to registration to **S0919**. Specimens must be submitted to the site's preferred cytogenetics laboratory (see [Section 15.1](#)).
- _____ p. Women of reproductive potential must have a negative pregnancy test within 14 days prior to registration. Patients must not be pregnant or nursing because of the teratogenic potential of the drugs used in this study. Women/men of reproductive potential must have agreed to use an effective contraceptive method.
- _____ q. Patients must have complete history and physical examination within 28 days prior to registration.
- _____ r. All patients must be informed of the investigational nature of this study and must sign and give written informed consent in accordance with institutional and federal guidelines.
- _____ s. As a part of the OPEN registration process (see Section 13.3 for OPEN access instructions) the treating institution's identity is provided in order to ensure that the current (within 365 days) date of institutional review board approval for this study has been entered in the system.

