5.2 Consolidation Registration (Step 2)

After completing Induction therapy, patients may be registered for Consolidation therapy **provided** that they were eligible for the initial registration and **satisfy** the following additional criteria at the time of Consolidation registration:

- _____ a. Patients must have achieved CR as defined in [Section 10.1c](#). Patients who achieved only CRi or PR, and patients who relapse from CR ([Section 10.3](#)) before this registration are not eligible.
- _____ b. Patients must not have symptomatic congestive heart failure, coronary artery disease, cardiomyopathy, or uncontrolled arrhythmias. Either an echocardiogram or MUGA scan with an ejection fraction $\geq 45\%$ must be obtained within 14 days prior to registration. (The same scan that was used during induction registration must be used for consolidation registration.) The ejection fraction must not have dropped $\geq 10\%$ from the baseline ejection fraction. If patient has had symptoms suggestive of ischemia or congestive heart failure after that cardiac evaluation was done, a repeat study must be obtained prior to registration.
- _____ c. Patients must have a serum creatinine < 2.0 mg/dl within 14 days prior to registration.
- _____ d. Patients must have a total bilirubin $\leq 2.0 \times$ Institutional Upper Limit of Normal (IULN) within 14 days prior to registration, unless the elevation is due primarily to elevated unconjugated hyperbilirubinemia secondary to Gilbert's syndrome or hemolysis and not to liver dysfunction.
- _____ e. Patients must have SGOT (AST) $\leq 3.0 \times$ IULN and SGPT (ALT) $\leq 3.0 \times$ IULN within 14 days prior to registration.
- _____ f. Patients must have Zubrod performance status of 0-2 (see **Section 10.8**).
- _____ g. Patients must not have a systemic fungal, bacterial, viral or other infection that is not controlled (defined as exhibiting ongoing signs/symptoms related to the infection and without improvement, despite appropriate antibiotics or other treatment).
- _____ h. Patients must have ANC $\geq 1,000/\text{mcl}$ and platelets $\geq 100,000/\text{mcl}$ within 7 days prior to registration.
- _____ i. Patients must be registered to Consolidation therapy (Step 2) within 60 days of beginning Induction therapy (with Day 1 being the start of Induction).

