8.2 Dose Modifications

- a. AraC: There is no standard dose modification for AraC. Dose modification in the setting of renal or hepatic dysfunction will be left to the discretion of the treating physician, but the Study Chair should be notified of any modifications, and these changes should be captured on the data form (treatment forms). Any modifications should be made based on labs obtained the day of drug administration. If dose modifications are required and toxicities subsequently resolve, AraC may be re-introduced in full dose for the next cycle.

AraC should be held for creatinine ≥ 2 mg/dl at any time during treatment.

Neurotoxicity exams should be performed prior to each dose of AraC. AraC should be held and no further doses administered if any signs of cerebellar neurotoxicity are found, and the Study Chair must be contacted.

- b. Idarubicin: Dosing of idarubicin will be based on the total bilirubin drawn the day of drug administration.

Bilirubin > 2.5 mg/dL but ≤ 5 mg/dL	50% reduction from full dose. Dose reductions will be based daily on bilirubin (and will be made based on full dose).
Bilirubin > 5 mg/dL	Hold idarubicin

Bilirubin should be checked the same day as the dose is due.

If dose modifications are required and toxicities subsequently resolve, idarubicin may be re-introduced in full dose for the next cycle.

- c. Pravastatin:

Grade 1 – 2 myalgia (Secondary to pravastatin)	Supplement with ubiquinone Q10 60 mg 4 x/day
Grade 3 – 4 myalgia (Pravastatin – related)	Hold pravastatin

- d. At each scheduled assessment during Consolidation Therapy, the following values must be met:

Serum creatinine < 2.0 mg/dl

Total bilirubin $\leq 2.0 \times$ IULN

SGOT and SGPT $\leq 3.0 \times$ IULN

If any of these values are elevated, treatment should be held until all values are within the allowable range.

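### The 45% ejection-fraction floor for entering Consolidation is not re-applied before cycle 2, so a patient with a low baseline can fall below it and still be treated

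*Combined protocol and SAP*

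**What the plan says.** The protocol sets EF requirements at three moments.

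- **Induction registration (Section 5.1, cardiac criterion).** EF must be at least 45%. The type of scan chosen is then fixed: "the same scan must be used throughout treatment and follow-up to monitor the patient for cardiac toxicity".
- **Consolidation registration (Section 5.2b).** EF must again be at least 45%, on a scan that "must be obtained within 14 days prior to registration", and must not have dropped by 10% or more from baseline. Section 5.2 introduces its list as "the following additional criteria at the time of Consolidation registration". There is one such registration, and Section 7.4 allows up to two cycles under it.
- **Before each Consolidation cycle (Sections 7.4 and 7.8c).** Section 7.4 says "ECHO or MUGA (whichever was performed at baseline) should be performed prior to each cycle of Consolidation therapy". Section 7.8c takes a patient off treatment for an EF drop of 10% or more "from baseline before either cycle of Consolidation therapy". It states no minimum EF.

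For cycle 2, Section 7.4 also requires continued remission, recovered neutrophils and platelets, and a start date: "The second cycle of Consolidation therapy must be initiated no sooner than 30 days and no later than 60 days" after cycle 1 began. Section 8.2d adds limits under the words "At each scheduled assessment during Consolidation Therapy, the following values must be met", but these are creatinine, bilirubin and transaminases only. Calendar 9.2 marks the scan in a separate Pre Cycle 2 column, after Week 5 of cycle 1. The scan's footnote fixes the type of test and gives neither an EF limit nor a number of days.

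**The concern.** Section 5.2b sets two EF limits side by side, a floor and a maximum drop, so the protocol itself does not treat the drop rule as enough for entry to Consolidation. Before cycle 2 only the drop rule remains. Other Step 2 conditions are carried forward explicitly (remission, counts, laboratory limits), and no reason is given for leaving out the floor.

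At stake is patient safety in a narrow group. An EF that would have kept a patient out of Consolidation at Step 2 does not, as written, stop a further course of idarubicin a cycle later, when the patient has had more anthracycline. Section 3.2b lists existing heart disease and earlier anthracycline treatment among the idarubicin warnings.

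**Working it through.** The plan gives no figure to reproduce here. The check asks which baselines allow an EF below 45 before cycle 2 without triggering 7.8c.

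**Inputs**

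- Lowest possible baseline: 45 (Section 5.1).
- EF at Step 2: at least 45, with a drop of less than 10% (Section 5.2b).
- Removal before cycle 2: a drop of 10% or more from baseline (Section 7.8c).
- Baseline is taken as the scan before Induction, and EF as a whole number.
- The protocol does not say whether 10% means EF points or a relative fall, so both are shown.

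**Formulas.** With baseline *b* and pre-cycle-2 EF *e*, the gap exists when *e* ≤ 44 and

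- points reading: *b* − *e* < 10, so the lowest passing *e* is *b* − 9;
- relative reading: *e* > 0.9*b*.

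**Results**

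| Baseline | Lowest EF passing 7.8c, points | Lowest EF passing 7.8c, relative |
|---|---|---|
| 45 | 36 | 41 (0.9 × 45 = 40.5) |
| 46 | 37 | 42 (41.4) |
| 47 | 38 | 43 (42.3) |
| 48 | 39 | 44 (43.2) |
| 49 | 40 | 45, no gap (44.1) |
| 53 | 44 | no gap |
| 54 | 45, no gap | no gap |

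The affected baselines are therefore 45-53 on the points reading and 45-48 on the relative reading. At the edges:

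- 53 to 44 is 9 points and passes; 54 to 44 is 10 points and is removed.
- 48 to 44 is 4/48 = 8.3% and passes; 49 to 44 is 5/49 = 10.2% and is removed.

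On a continuous scale the bounds are baselines below 45 + 10 = 55 (points) or below 45/0.9 = 50 (relative).

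**Example on both readings.** From baseline 46 to EF 43 is 3 points, or 3/46 = 6.5%. Section 7.8c is not met, yet EF 43 would have failed 5.2b.

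**What the lowest values require.** The patient must have had an EF of at least 45 at Step 2. Reaching 36 or 41 from baseline 45 therefore means a fall of at least 9 or 4 points between the Step 2 scan and the cycle 2 scan.

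**Idarubicin exposure on protocol.** Induction gives 12 × 3 = 36 mg/m² by Step 2. Cycle 1 adds 12 × 2 = 24, making 60 mg/m² before cycle 2. This reads the dose in the 7.4 table as daily, since calendar 9.2 marks both days. If it were a cycle total, the sum would be 36 + 12 = 48 mg/m².

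**The case against.** The best defence is that this is a recognisable structure: an absolute floor at entry, then a change-from-baseline rule for continuing. Cycle 2 does have a cardiac gate, with a mandatory repeat scan and a removal rule written for both cycles. A reader might infer that cycle 2 goes ahead with no cardiac check. The documents do not support that, and for baselines of 54 or more (points) or 49 or more (relative) the drop rule alone keeps EF at 45 or above. Nor does the missing floor contradict any other section. All of this stands. It does not explain why the floor counts at the start of cycle 1 and not at the start of cycle 2.

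A second defence is clinical judgement. Serial scans are there to watch for cardiac toxicity, and 7.8d allows removal for unacceptable toxicity. That plausibly covers symptomatic heart failure. It gives no EF value, so an asymptomatic fall below 45% depends on the physician invoking it. The note to 5.1m, "the risk versus benefit of therapy should be weighed, particularly in the setting of receiving consolidation therapy", reaches only patients with a prior malignancy who had anthracyclines or mediastinal or pericardial radiation.

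On timing, a reader might infer that the cycle 2 scan could be taken at any point after the cycle 1 idarubicin. The calendar does not support that: it places the scan in the Pre Cycle 2 column and leaves the cycle 1 day columns unmarked. What remains is that no number of days is stated. The calendar note also defers to external SWOG guidelines. Their content is not in the documents, and the note's list does not name cardiac scans, so they may or may not supply a window.

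Finally, the documents are marked closed to accrual, which limits the practical benefit for this trial. The wording would still matter if the regimen went on to the Phase III investigation named in Section 1.1.

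**Conclusion.** The concern holds, as a minor point. Before Consolidation cycle 2 a patient with a baseline EF of 45-53 (points) or 45-48 (relative), who satisfied the floor at Step 2, can be below 45% without meeting 7.8c and, as written, still receive idarubicin unless the physician applies 7.8d. The ranges assume whole-number EF and a baseline taken before Induction.

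The number affected cannot be estimated, because the documents give no EF distribution. It may be zero: such a patient must reach CR (CRi is not enough for Step 2), complete cycle 1, keep remission and counts, and fall below 45 within a narrow band. A reader might also infer some effect on the efficacy conclusion. There is none, since the CR/CRi endpoint is assessed after Induction.

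**What to change.** In Sections 7.4 and 7.8c, require before each Consolidation cycle both an EF of at least 45% and a drop of less than 10% from baseline, read on the ECHO or MUGA already scheduled. Preferably, require that scan to be dated within 14 days before the cycle, matching the length of the 5.2b window, and put the same number in the calendar 9.2 footnote. In 5.2b and 7.8c, state whether 10% means EF points or a relative fall.

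For the floor and the definition, the cost is wording only, as the scan is already required. The 14-day window may occasionally mean repeating a scan done early. The real downside is that a few patients with low baseline EF may lose the second Consolidation cycle.

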7.9 Discontinuation of Treatment

All reasons for discontinuation of treatment must be documented in the Off Treatment Notice.

7.10 Follow-Up Period

All patients will be followed until death or 5 years after initial registration, whichever occurs first.

8.0 TOXICITIES TO BE MONITORED AND DOSAGE MODIFICATIONS

8.1 NCI Common Terminology Criteria for Adverse Events

Two different versions of the NCI Common Terminology Criteria for Adverse Events (CTCAE) will be used on this study.

- a. Serious Adverse Event (SAE) reporting

The CTCAE (NCI Common Terminology Criteria for Adverse Events) Version 4.0 will be utilized **for SAE reporting only**. The CTCAE Version 4.0 is identified and located at the CTEP website at http://ctep.cancer.gov/protocolDevelopment/electronic_applications/ctc.htm. All appropriate treatment areas should have access to a copy of the CTCAE Version 4.0.

b. Routine toxicity reporting

This study will utilize the CTCAE Version 3.0 for routine toxicity reporting. A copy of the CTCAE Version 3.0 can be downloaded from the CTEP home page (<http://ctep.cancer.gov>). All appropriate treatment areas should have access to a copy of the CTCAE Version 3.0.

